3 SCHEDULE OF ASSESSMENTS

Schedules of assessments for Cohort 1 and Cohort 2 are in Table 3-1 through Table 3-3. All visits will be scheduled relative to the Day 1 Visit.

Subjects may choose to complete all screening assessments within the 28-day Screening Period or they may choose a 2-step screening process and first complete only the *APOL1* genotype assessment at any time before Day -1 (including before Day -28), followed by the rest of the screening assessments during the 28-day Screening Period. The informed consent form (ICF) will outline the screening options. Additional information is provided in Section 9.1.1. Informed consent must be completed before any assessments are done at the Screening Visit. The SF-36 must be completed before any other assessment when they are required. Other assessments may be performed in any order when more than 1 assessment is required at a particular time point, unless noted otherwise. All assessments will be performed before dosing, unless noted otherwise.

Table 3-1 Study VX19-147-101: Screening

Event/Assessment	Optional Genotype Screening Visit (Before Day -1)	Screening Period (Day -28 to Day -1)	Comments			
Subject visit	X	X	Activities may be performed by a home health visit or in the clinic, unless otherwise noted (Section 9.3.5). The complete physical exam must be done by the investigator (Section 11.6.3). The Screening Visit should occur in the clinic if possible, but home health may be used if extenuating circumstances prevent a clinic visit (Section 9.1.1).			
Informed consent	X	X	Informed consent must be obtained before any study-related procedures. It may be obtained in person or remotely, and it may be collected before the first visit (Section 13.2.2).			
Demographics		X				
Medical history		X				
Medications review		X	Section 9.4			
Standard 12-lead ECG		X	To be performed in triplicate after the subject has been supine for at least 5 minutes. When ECGs, vital signs, and blood draws coincide, they should be performed in said order. (Section 11.6.4).			
Vital signs		X	Vital signs will be collected after the subject has rested for at least 5 minutes. Blood pressure must be collected in triplicate. (Section 11.6.3).			
Height and weight		X	Weight and height will be measured with shoes off with light weight clothing (no outerwear). BMI will be calculated using height and weight (Section 11.1).			
Physical examination		X	A complete exam will be done if the visit occurs in the clinic. If the visit occurs using a home health nurse, an abbreviated exam will be done (Section 11.6.3).			

Table 3-1 Study VX19-147-101: Screening

Event/Assessment	Optional Genotype Screening Visit (Before Day -1)	Screening Period (Day -28 to Day -1)	Comments			
Serum FSH (suspected postmenopausal female subjects only)		X	A blood sample will be collected (Section 11.6.2).			
Serum β-hCG (all female subjects)		X	A blood sample will be collected (Section 11.6.2).			
Serum chemistry		X	A blood sample will be collected (Section 11.6.2).			
Hematology		X	A blood sample will be collected (Section 11.6.2).			
Coagulation		X	A blood sample will be collected (Section 11.6.2).			
Serology (HIV-1 and HIV-2 Antibodies)		X	A blood sample will be collected (Section 11.6.2).			
Hepatitis B surface antigen		X	A blood sample will be collected (Section 11.6.2).			
HCV test		X	A blood sample will be collected (Section 11.6.2).			
Confirmation of APOL1 genotype	X	X	A genotyping sample will be collected if a result is not available using a Vertex-approved clinical study assay (Section 9.1.1).			
Urine sample		X (3 samples)	Collected after signing the informed consent for use in efficacy, biomarker, and safety analyses (Sections 11.3 and 11.6.2). The first morning void will be collected for 3 independent samples, which are collected on 3 separate days within a 7-day period. The third sample must be collected by Day -5 to allow confirmation that UPCR values meet eligibility criteria (Section 8.1). Refer to sample handling guidelines to ensure samples are submitted appropriately for analysis.			
Adverse events	Continuous fron through		For subjects undergoing a 2-step screening process, AEs related to phlebotomy will be collected for up to 24 hours after the blood collection; AEs will not be collected during the time between a subject undergoing genotype screening and the start of the Screening Visit. Additional information about AE reporting is provided in Section 11.6.1.			

Protocol VX19-147-101, Version 6.0

Table 3-2 Study VX19-147-101: Part A Treatment Period 1, Treatment Period 2, and Early Termination of Treatment Visit

	Treatmen	t Period 1		Trea	atment Perio	od 2			
	Day 1 Visit	Week 1 Visit	Day 15 Visit	Week 3 Visit	Week 5 Visit	Week 9 Visit	Week 13 Visit	Early	
Event/ Assessment ^a	Window: Day 1 (±0 days)	Window: Day 8 (±1 day)	Window: Day 15 (±2 days)	Window: Day 22 (±2 days)	Window: Day 36 (±2 days)	Window: Day 64 (±2 days)	Window: Day 92 (-2 days)	Termination of Treatment Visit ^b	Comments
Subject visit	X	X	X	X	X	X	X	X	All visits may be performed by a home health visit or in the clinic at the discretion of the investigator (Section 9.3.5). All visits must have a consultation between the subject and investigator (i.e., in person, phone, or telemedicine video conference) within 1 business day after the home health visit, which can be outside the visit window.
SF-36	X				X		X	X	To be completed before all other study assessments (Section 11.5.3).
Standard 12-lead ECG	X	Х	X	X	X	X	X	X	Complete predose after SF-36 and before other assessments. The subject should be supine for at least 5 minutes before the start of ECG. When ECGs, vital signs, and blood draws coincide, they should be performed in said order. On Day 1 and Day 15, an ECG (Section 11.6.4) will also be collected 2 (± 1) hours postdose.
Vital signs	Х	Х	X	X	X	Х	X	X	Complete before the assessments listed in rows below. The subject should rest for at least 5 minutes before the start of vital sign collection and they should be seated during the assessment (Section 11.6.3). Blood pressure will be collected in triplicate.
Weight	X	X	X	X	X	X	X	X	Weight will be measured with shoes off and light weight clothing (no outerwear) (Section 11.1).

^a All assessments will be performed before dosing unless noted otherwise.

If the subject prematurely discontinues study treatment during the Treatment Period, an ETT Visit should be scheduled as soon as possible after the subject decides to terminate study treatment. If the ETT Visit occurs 3 weeks or later following the last dose of study drug, then the ETT Visit will replace the SFUV, and a separate SFUV will not be required. After the ETT Visit, subjects will not complete further Part A Visits; these subjects will not continue to Part B (Table 3-3).

Protocol VX19-147-101, Version 6.0

Table 3-2 Study VX19-147-101: Part A Treatment Period 1, Treatment Period 2, and Early Termination of Treatment Visit

	Treatment Period 1		Treatment Period 2					 	
	Day 1 Visit	Week 1 Visit	Day 15 Visit	Week 3 Visit	Week 5 Visit	Week 9 Visit	Week 13 Visit	Early Termination of Treatment Visit ^b	
Event/ Assessment ^a	Window: Day 1 (±0 days)	Window: Day 8 (±1 day)	Window: Day 15 (±2 days)	Window: Day 22 (±2 days)	Window: Day 36 (±2 days)	Window: Day 64 (±2 days)	Window: Day 92 (-2 days)		Comments
Abbreviated Physical examination	X	X	Х	X	X	X	Х	X	In addition to the scheduled visits, symptom-directed physical examinations will occur at any time during the study if triggered by AEs or if deemed necessary by the investigator (Section 11.6.3).
Serum chemistry	X Fasted	X	X	X Fasted	X	X	X Fasted	X Fasted	A blood sample will be collected predose after an overnight fast on indicated days. All other days do not require fasting. (Section 11.6.2).
Hematology	X	X	X	X	X	X	X	X	A blood sample will be collected (Section 11.6.2).
Coagulation	X	X	X	X	X	X	X	X	A blood sample will be collected (Section 11.6.2).
Biomarker blood sample	X	X	X	X	X	X	X	X	Section 11.5.1.
VX-147 PK blood sample	intensive	predose	intensive	predose	intensive	predose	X	X	A blood sample will be collected (Section 11.2.1). Intensive PK sampling Day 1, Day 15, Week 5: predose (within 60 min before dosing) and 0.25, 0.5, 1, 2, 4 and 12 hours postdose Post treatment samples (Week 13 and ETT): A single sample collected anytime during the Visit.

Protocol VX19-147-101, Version 6.0

Table 3-2 Study VX19-147-101: Part A Treatment Period 1, Treatment Period 2, and Early Termination of Treatment Visit

	Treatmen	t Period 1 Treatment Period 2					 		
	Day 1 Visit	Week 1 Visit	Day 15 Visit	Week 3 Visit	Week 5 Visit	Week 9 Visit	Week 13 Visit	Early	
Event/ Assessment ^a	Window: Day 1 (±0 days)	Window: Day 8 (±1 day)	Window: Day 15 (±2 days)	Window: Day 22 (±2 days)	Window: Day 36 (±2 days)	Window: Day 64 (±2 days)	Window: Day 92 (-2 days)	Termination of Treatment Visit ^b	Comments
Urine sample β-hCG (urine)	Х°	X	X	X	X (3 samples)	X (3 samples)	X (3 samples)	X	The first morning urine void (predose) will be collected and used for efficacy, safety, and biomarker analyses (Sections 11.3 and 11.6.2). During Week 5, Week 9, and Week 13, 3 samples will be collected on 3 separate days within a 7-day period. If the subject forgets to collect the first morning void on the day of the visit, they may provide this sample predose on a different day within the visit window. Refer to sample handling guidelines to ensure samples are submitted appropriately for analysis. All female subjects of childbearing potential
p-nCG (urine)	X				X	X	X	X	(Sections 11.6.2 and 11.6.5). This can be collected in the same sample as the urine sample for efficacy, safety, and biomarker analysis.
VX-147 dosing				X		The last dose of Treatment Period 1 will be Day 14. The first dose of Treatment Period 2 will be on Day 15 after all predose assessments are completed. The last day of dosing will occur the day before the Week 13 visit. The first dose in each period must be administered under the supervision of site medical staff or a home health nurse. Subjects will be monitored for 4 hours after receiving the first dose of each Treatment Period. (Section 9.6).			

^c Day 1 urinalysis will be for safety and biomarker assessments. Efficacy assessments will not be done.

Protocol VX19-147-101, Version 6.0

Table 3-2 Study VX19-147-101: Part A Treatment Period 1, Treatment Period 2, and Early Termination of Treatment Visit

	Treatmen	nt Period 1		Trea	atment Perio	od 2			
	Day 1 Visit	Week 1 Visit	Day 15 Visit	Week 3 Visit	Week 5 Visit	Week 9 Visit	Week 13 Visit	Early	
Event/ Assessment ^a	Window: Day 1 (±0 days)	Window: Day 8 (±1 day)	Window: Day 15 (±2 days)	Window: Day 22 (±2 days)	Window: Day 36 (±2 days)	Window: Day 64 (±2 days)	Window: Day 92 (-2 days)	Termination of Treatment Visit ^b	Comments
Adverse events			Continu	ous from signi	ng of ICF th	rough SFUV			Section 11.6.1.
Medications review			Continu	ous from signi	ing of ICF th	rough SFUV			Section 9.4.

Table 3-3 Study VX19-147-101: Postdose PK Sampling, Safety Follow-up Visit, and Part B Off-treatment Follow-up Period

Event/Assessment	Postdose PK Sampling	SFUV 28 (± 7) Days	Part B: Optional Off-treatment Follow-up	Comments
	(Approximately 48 hours after the last dose of study drug) ^a	After Last Dose of Study Drug ^b	Visits ^c (Part B Week 4 ^b , 8, and 12)	
Subject visit	X	X	X (until UPCR returns to ≥90% of baseline level)	The visit may be performed by a home health visit or in the clinic at the discretion of the investigator (Section 9.3.5). For each visit, at least 1 interaction with the subject and investigator will occur by phone, video, or in the clinic (i.e., in person, phone, or telemedicine video conference) within 1 business day after the home health visit, which can be outside the visit window. See Section 9.1.3 for details about determining the last visit for Part B.
SF-36		X		To be completed before all other study assessments (Section 11.5.3).
Standard 12-lead ECG		X		Complete after SF-36 and before other assessments after subject has been supine for at least 5 minutes. ECGs (Section 11.6.4), vital signs, and blood draws should be performed in said order.
Vital signs		X		Complete before other assessments listed below after subject has been at rest for at least 5 minutes; they should be seated during the assessment (Section 11.6.3). Blood pressure will be collected in triplicate.

^a The postdose PK sampling visit is required for all subjects, with the exception of those who complete an ETT Visit.

The SFUV and Part B Week 4 Off-treatment Follow-up Visit may occur on the same day, provided the visit windows are met for both visits.

Visit windows for Part B are as follows: Week 4 Visit (Day 120 ± 2 weeks), Week 8 Visit (Day 148 ± 2 weeks), Week 12 Visit (Day 176 ± 2 weeks).

Table 3-3 Study VX19-147-101: Postdose PK Sampling, Safety Follow-up Visit, and Part B Off-treatment Follow-up Period

On-treatment Follow-up reriou					
Event/Assessment	Postdose PK Sampling (Approximately 48 hours after the last dose of study drug) ^a	SFUV 28 (± 7) Days After Last Dose of Study Drug ^b	Part B: Optional Off-treatment Follow-up Visits (Part B Week 4 ^b , 8, and 12)	Comments	
Weight		X		Weight will be measured with shoes off and light weight closing (no outerwear). (Section 11.1).	
Abbreviated physical examination		X		In addition to the scheduled visits, symptom-directed physical examinations will occur at any time during the study if triggered by AEs or if deemed necessary by the investigator (Section 11.6.3).	
Serum chemistry		X Fasted		A blood sample will be collected following an overnight fast (Section 11.6.2).	
Hematology		X		A blood sample will be collected (Section 11.6.2)	
Coagulation		X		A blood sample will be collected (Section 11.6.2)	
VX-147 PK Sampling	X			A blood sample will be collected (Section 11.2.1).	
Urine sample		X	X	The first morning urine void will be collected and used for efficacy, safety, and biomarker analyses (Sections 11.3 and 11.6.2). Refer to sample handling guidelines to ensure samples are collected and submitted appropriately for analysis.	
β-hCG (urine)		X		All female subjects of childbearing potential (Section 11.6.2). This can be collected in the same sample as the other urine sample.	
Adverse events		gning of ICF through UV	NA	Section 11.6.1	
Medications review		igning of ICF through ollow-up visit, whichev	SFUV or last off-treatment ver is later	May be collected via telemedicine (Section 9.4)	

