9.6 Administration

VX-147 will be administered as 15 mg tablets, orally, as shown in Table 3-2.

Study drug will be administered according to the following guidelines:

- The first dose in each period must be administered under the supervision of site medical staff
 or a home health nurse. Subjects will be monitored for 4 hours after receiving the first dose
 of each Treatment Period
- On days of scheduled visits, the dose of study drug will be administered after predose assessments have been completed.
- Study drug will be taken at approximately the same time on each dosing occasion. For example, subjects that administer VX-147 dose at 8AM on Day 1 should administer all subsequent doses at 08:00AM ± 2 hours.
- Study drug may be taken with or without food.
- Subjects will swallow the study drug whole, with a full glass of water and will not chew it before swallowing.
- On days of intensive PK sampling, the date, dose taken, and time of study drug administration will be recorded for the 2 doses before PK sample collection and on the morning of PK sample collection.
- Subjects will be instructed to bring all used and unused materials associated with the study drug to the site or the nurse will take these materials at each study visit; study drug will be dispensed at each visit, as appropriate.

Missed Doses

If a subject misses a dose and recalls the missed dose within 6 hours, the subject should take his/her dose according to the guidance above. If more than 6 hours have elapsed after his/her usual dosing time, the subject should skip that dose and resume his/her normal schedule for the following dose. An example is provided below:

• If the morning dose of study drug should have been taken at approximately 08:00AM, and the subject remembers at 12:00PM that he/she forgot to take his/her dose, he/she should take the dose as soon as possible. If they remember after 2:00PM that they forgot to take the morning dose, they should skip that dose and resume the normal schedule the next day.

Additional information is provided in the Pharmacy Manual.

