11.6.2 Clinical Laboratory Assessments

The safety laboratory test panels are shown in Table 11-2. For purposes of study conduct, blood and urine samples will be analyzed at a central laboratory, with the exception of urine pregnancy tests and if there are extenuating circumstances due to COVID-19, as described below.

Urine samples for safety laboratory assessments may be collected at the same time as the urine samples for efficacy and biomarker assessments (See Section 11.3). Refer to sample handling guidelines to ensure that each sample collected is submitted appropriately to the lab for analysis at each visit. At the Screening, Week 5, Week 9, and Week 13 Visits, only the third urine sample will be used for safety urinalysis and biomarker assessments; urine protein, creatinine, and albumin will be assessed for all 3 samples collected during this visit.

On days when overnight fasts are required (see Table 3-2 and Table 3-3), subjects will abstain from food and beverages for 8 hours before the start of the visit. During this period, water may be consumed up to 1 hour before study drug administration.

Local laboratories may be used at the discretion of the local investigator for management of urgent medical issues. If a local laboratory test value is found to be abnormal and clinically significant, it will be verified by the central laboratory as soon as possible after the investigator becomes aware of the abnormal result. If it is not possible to send a timely specimen to the central laboratory (e.g., the subject was hospitalized elsewhere), the investigator may base the assessment of an AE on the local laboratory value. Laboratory test results that are abnormal and considered clinically significant will be reported as AEs (see Section 13.1).

The central laboratory should be used for all assessments when possible, and Vertex should be notified if a local laboratory is to be used. If the subject is unable to have a clinic or home health visit due to extenuating circumstance of the COVID-19 global pandemic, local laboratories may be used after Day 1 for blood safety samples. When local labs are used for blood safety sample collection, the site will obtain the results from the local lab and ensure data are captured in the electronic data capture (EDC) per Section 13.5. Local labs may not be used for screening assessments.

Table 11-2	Safety	Laboratory	Test Pa	anels
-------------------	--------	------------	---------	-------

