Serum Chemistry	Hematology	Urinalysis ^a	
Glucose	Hemoglobin	Leukocyte esterase	
Blood urea nitrogen ^b	Hematocrit	Nitrite	
Creatinine	Erythrocytes	Urine protein ^c	
Creatine kinase	Mean corpuscular volume	Urine creatinine ^c	
Sodium	Platelets	Urine albumin ^c	
Potassium	Reticulocytes	Urine blood	
Calcium	Leukocytes		
Chloride	Differential (absolute and percent):		
Magnesium	Eosinophils	Urine ketones	
Bicarbonate	Basophils	Urine glucose	
Phosphate	Neutrophils	Urobilinogen	
Total bilirubin, direct bilirubin	Lymphocytes	Urine pH	
Alkaline phosphatase	Monocytes	Specific gravity	
Aspartate transaminase	Blood smear ^e		
Alanine transaminase	Coagulation		
Amylase	Activated partial thromboplastin time		
Lipase	Prothrombin time		
Gamma-glutamyl transferase	Prothrombin time International		
Protein	Normalized Ratio		
Albumin			
Cholesterol ^d			
Triglycerides ^d			
Low-density lipoprotein-direct ^d			
High-density lipoprotein ^d			

^a For the Day 1 predose sample, microscopic examination of urine will be done, and results will be provided for leukocytes, erythrocytes, crystals, bacteria, and casts.

Additional Tests at Screening: The following additional tests will be performed during screening to assess eligibility:

- *Serum beta-human chorionic gonadotropin (\beta-hCG) for all subjects*: Serum samples will be analyzed for β -hCG at the central laboratory.
- Follicle-stimulating Hormone (Screening Period only): Blood sample for FSH will be measured for any suspected postmenopausal female with at least 12 months of continuous spontaneous amenorrhea. Serum FSH levels must be within the postmenopausal reference range of the performing laboratory to be considered postmenopausal.
- *APOL1*: A blood sample will be collected to determine *APOL1* genotype, if required per Table 3-1.
- *HIV-1 and HIV-2 antibodies:* A blood sample will be collected for serology.
- Hepatitis B surface antigen: A blood sample will be collected for serology.

b If blood urea nitrogen cannot be measured, urea may be substituted.

eGFR will be calculated using the CKD-EPI equation, and AKI will be determined using KDIGO criteria. 24 Urine protein, creatinine, and albumin measurements will be used for efficacy and safety.

d Lipid profile will only be measured at the visits with fasting: Day 1, Week 3, Week 13, ETT, and SFUV.

^e A blood smear will be collected on Day 1, Week 13, and the ETT Visit.

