9 STATISTICAL ANALYSIS

9.1 General Considerations

The Schedule of Assessments is provided in Section 3 of the CSP. The precision standards for reporting variables are provided in an internal Biometrics document that specifies the programming rules including the precision for derived variables.

Continuous variables will be summarized using the following descriptive summary statistics: the number of subjects (n), mean, SD, median, minimum value (min), and maximum value (max).

Categorical variables will be summarized using counts and percentages.

Baseline value, unless specified otherwise, will be defined as the most recent non-missing measurement (scheduled or unscheduled) collected before the first dose of study drug in the Treatment Period. For ECGs, baseline will be defined as the most recent pretreatment measurement (or the average of triplicate measurements, if the most recent pretreatment measurement is obtained in triplicate) before the first dose of study drug in the Treatment Period. For systolic and diastolic blood pressure, baseline will be defined as the most recent pretreatment measurement (or the average of triplicate measurements, if the most recent pretreatment measurement is obtained in triplicate) before the first dose of study drug in the Treatment Period. For UPCR (and UACR) data baseline value will be the average of UPCR (UACR) values from the 3 urine samples collected during screening for the purpose of assessing eligibility.

Change (absolute change) from baseline will be calculated as Post-baseline value – Baseline value.

Treatment-emergent (TE) Period will include the time from the first dose of study drug in the Treatment Period to either (1) the Safety Follow-up Visit, (2) ETT Visit if it replaces the Safety Follow-up Visit, or (3) the date of the last dose + 28 days for subjects who do not have a Safety Follow-up Visit. The TE Period will be used for safety analyses unless specified otherwise.

Unscheduled visits: Data obtained from unscheduled visits will be included in the analysis as follows:

- In scheduled visit windows per specified visit windowing rules
- In the derivation of baseline
- In the derivation of maximum and minimum values during TE period, and maximum and minimum change from baseline values during TE period for safety analyses
- In individual subject data listings as appropriate

Visit Window: The analysis visit windows for the protocol-defined visits are provided in [Appendix A](#).

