9.4.2 Clinical Laboratory

All statistical analyses of laboratory values will be performed using SI units. For treatment-emergent laboratory measurements, the observed values and change from baseline values of the continuous hematology, chemistry, and coagulation results will be summarized at each visit.

The number and percentage of subjects with selected test values meeting at least 1 threshold analysis criterion event during the TE period will be summarized. The threshold analysis criterion shift from baseline will also be summarized for selected laboratory test values. The threshold analysis criteria are provided in [Appendix D](#).

Results of urinalysis and the urine/serum pregnancy test will be in individual subject data listings only.

In addition, a listing of individual subject hematology, chemistry, and coagulation values outside the normal reference ranges will be provided. This listing will include data from both scheduled and unscheduled visits.

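### Glucose change from baseline sets samples with no fasting requirement (Week 1, Day 15, Week 5, Week 9) against a baseline that is normally fasted, so those by-visit summaries can include a meal effect

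*Protocol*

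**What the plan says.** All protocol references are to Version 6.0.

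- **Sampling.** Glucose is in the serum chemistry panel (Table 11-2), which is drawn at every Part A visit and at the SFUV. Table 3-2 marks chemistry as fasted at Day 1, Week 3, Week 13 and the ETT visit, and Table 3-3 does so at the SFUV. For the rest, the Table 3-2 comment applies: "A blood sample will be collected predose after an overnight fast on indicated days. All other days do not require fasting".
- **Meaning of fasting.** Section 11.6.2 says that on days when a fast is required, "subjects will abstain from food and beverages for 8 hours before the start of the visit".
- **Lipids.** Table 11-2 carries a restriction for them: "Lipid profile will only be measured at the visits with fasting: Day 1, Week 3, Week 13, ETT, and SFUV". Glucose has no such note.
- **Baseline.** SAP 9.1: "Baseline value, unless specified otherwise, will be defined as the most recent non-missing measurement (scheduled or unscheduled) collected before the first dose". No exception is made for glucose.
- **Analysis.** SAP 9.4.2 states that "the observed values and change from baseline values of the continuous hematology, chemistry, and coagulation results will be summarized at each visit". It adds that "a listing of individual subject hematology, chemistry, and coagulation values outside the normal reference ranges will be provided". Neither sentence mentions fasting.

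**The concern.** Glucose responds to food. When the baseline is taken fasted and a later sample may not be, the difference between them can contain a meal effect as well as any effect of treatment. The plan avoids this for lipids by measuring them only at fasting visits, but leaves glucose, from the same panel, in the all-visit change summary.

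Laboratory values are a secondary endpoint, and every subject receives VX-147. No control arm is available to subtract a sampling effect. Each cohort has about 10 subjects, so a few fed samples can move a visit mean. A reader of the table could take a rise at the four visits for a drug signal, or dismiss a real rise there as food. Nothing in the table or the listing would say which samples came from visits where a fast was required.

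**Working it through.** The plan states no figure on this point to reproduce. The check is a trace of schedule, baseline and analysis, followed by an illustration of size.

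**1. Visit by visit, against a fasted Day 1 baseline** (Tables 3-2 and 3-3; dosing from Table 3-2)

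| Visit | Fast required | Treatment at the time of the sample | Comparison |
|---|---|---|---|
| Week 1 | No | 15 mg | Mixed |
| Day 15, predose | No | 15 mg | Mixed |
| Week 3 | Yes | 45 mg | Like for like |
| Week 5 | No | 45 mg | Mixed |
| Week 9 | No | 45 mg | Mixed |
| Week 13 | Yes | 45 mg | Like for like |
| SFUV | Yes | Off drug | Like for like |

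Four of the 6 scheduled Part A post-baseline visits are mixed, or 4 of 7 with the SFUV.

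**2. Does another rule make the four visits fasted in effect?** No. Table 3-2 says "All assessments will be performed before dosing unless noted otherwise", but Section 9.6 says "Study drug may be taken with or without food". A predose sample can therefore follow a meal.

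**3. Size.** Let *p* be the share of subjects who have eaten before the sample and *m* the mean rise in glucose from eating. With a fasted baseline and no drug effect:

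expected mean change = *p* × *m*

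The documents give neither quantity. As a pure assumption, take *m* from 0.5 to 2.0 mmol/L and *p* from 0 to 1:

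| *p* | *m* = 0.5 | *m* = 1.0 | *m* = 2.0 |
|---|---|---|---|
| 0 | 0 | 0 | 0 |
| 0.25 | 0.125 | 0.25 | 0.5 |
| 0.5 | 0.25 | 0.5 | 1.0 |
| 0.75 | 0.375 | 0.75 | 1.5 |
| 1 | 0.5 | 1.0 | 2.0 |

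The spurious mean change runs from 0 to 2.0 mmol/L over this grid. At Week 3 and Week 13 it is 0, given a fasted baseline.

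**4. When the baseline is not the Day 1 sample.** If the Day 1 glucose is missing, SAP 9.1 falls back on an earlier predose value. Screening chemistry (Table 3-1) has no fasting requirement. A subject who ate before that sample has a baseline raised by that meal's effect, which biases the change at fasted visits downward by the same amount.

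**5. How samples reach the analysis visits.** SAP Appendix A assigns chemistry to visits by study-day window, admits unscheduled samples and keeps the one nearest the target day. An unscheduled sample with no fasting requirement can therefore fill the Week 3 or Week 13 row. A fasted ETT sample can land in the Week 5 or Week 9 row, because ETT is not an analysis visit of its own. It maps to Safety Follow-up only when it falls 21 days or more after the last dose and there is no nominal follow-up visit.

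**6. Which outputs are touched.** Appendix D, Table 12-3, has no glucose criterion, so no threshold or shift table is affected. What remains is the by-visit summary and the out-of-range listing.

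**The case against.** The strongest reply is that little turns on this. Safety analysis is descriptive, without hypothesis tests, and no decision rule uses glucose. Keeping glucose in an all-visit safety panel is a defensible choice, since a non-fasted value still serves monitoring, and treating lipids differently is not a contradiction. All of that stands, and it limits the point to one of presentation.

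Two stronger readings are tempting, and the documents support neither.

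- *That a drug effect on glucose cannot be separated from the sampling condition.* Week 3, Week 13 and the SFUV are fasted. They cover one week on 45 mg, the end of treatment and the off-drug period. A rise at the four other visits that vanishes at Week 3 and Week 13 would itself point to food. Permitted corticosteroids and tacrolimus do not change this much: Protocol 9.4 requires stable dosing from before screening through Week 13 or ETT, so a steady effect is already in the baseline. The allowance for higher corticosteroid doses in urgent comorbid conditions is a narrow exception.
- *That the samples at the four visits are fed.* Fasting is not required there, but it is not excluded. Samples are predose, and the dosing example in Section 9.6 is 8 AM, so some subjects may well still be fasted.

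A simple visit filter is also open to objection. It would not reliably select fasted samples under the Appendix A windows, and it would remove Week 1 and Day 15, the only visits that reflect 15 mg. The fix has to allow for both.

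**Conclusion.** The point holds as a minor one. At 4 of 6 scheduled Part A post-baseline visits, the planned glucose change compares a sample with no fasting requirement with a baseline that is normally fasted, and neither document adjusts for this or labels it. The resulting bias is upward or zero. Its size cannot be fixed from the documents; the 0 to 2.0 mmol/L range rests wholly on assumed meal effects and shares.

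The conclusion assumes that the Day 1 glucose is present, that the fast is kept where required, and that scheduled samples fill the analysis windows. The primary endpoint and the threshold analyses are untouched, and the fasted visits still allow glucose to be assessed.

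**What to change.** Amend SAP 9.4.2 for glucose as follows:

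1. Base the interpretable change-from-baseline summary on samples from nominal visits that require a fast (Week 3, Week 13, SFUV, and ETT under its own nominal label), or on recorded fasting status if it is collected. Do not select by the Appendix A window alone.
2. Use the glucose value from the fasted Day 1 visit as baseline for this summary, with no fallback to screening.
3. Present Week 1, Day 15, Week 5 and Week 9 glucose separately, labelled 'fasting not required'.
4. Carry the same label into the out-of-range listing.

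No new data are needed. The costs are a short SAP amendment and some extra programming for one analyte, and a subject without a Day 1 glucose drops out of the change summary. The main loss is that the 15 mg period (Week 1 and Day 15 predose) has no like-for-like glucose change summary. No analysis can supply one, unless fasting status was recorded and enough of those samples prove to be fasted.
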